10.2.1. Pre-Randomization Assessments

The following assessments must be completed at Visit 2 to confirm that the patient is eligible for randomization. Upon arrival at the clinic, the following assessments should be done, in the following general order:

- Assess occurrence of adverse events
- Update medical history (with changes since screening noted)
- Assess changes in medication history and concomitant medications
- Obtain vital signs and weight
- Administer CAPS-5 - “Symptom Severity Version”, using 1-week recall
- Conduct urine drug screen (urine dipstick, only as necessary, if select Visit 1 tests were positive for excluded medications that required discontinuation prior to randomization)
- Conduct urine pregnancy test (for women of child-bearing potential)
- Perform visual examination of the oral cavity
- Have the patient complete the following outcome scales (in order):
 - SDS
 - PROMIS scale for sleep disturbance
 - CSFQ-14
- Administer the MADRS
- Administer the C-SSRS- Since Last Visit Version
- Physician to assess CGI-S (needs to be completed once all other assessments are available for investigator to review)

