13. STATISTICS

A full description of the statistical analyses to be performed at study completion will be provided in a Statistical Analysis Plan (SAP) prior to unblinding.

Baseline will be defined as those values recorded closest to, but prior to administration of the first dose of study drug.

Unless otherwise noted, significance tests of treatment differences will be tested at the two-sided 0.05 level.

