13.4.3. Secondary Efficacy Analyses

MMRM methodology will be utilized for the continuous secondary endpoints, and analyses will be based on the mITT population. The dependent variable will be the observed change from baseline in the respective secondary endpoint at each post-randomization visit, with the exception of those measures that do not have a baseline. Covariates in the model will include the fixed categorical effects of treatment, site, sex, visit and treatment by visit interaction (baseline score and baseline score by visit interaction will be included as appropriate).

Binary data will be analyzed using a Cochran-Mantel-Haenszel (CMH) test controlling for the randomization stratification of sex, analyzed separately at each visit. Patients with missing data will be analyzed as though they are non-responders. Odds ratios and corresponding 95% confidence intervals will be presented.

To adjust for multiplicity and to control for overall type I error, a sequential test procedure will be applied to the key secondary efficacy endpoints. If the primary analysis produces a result that is statistically significant, a nominal significance level will be used for comparing the secondary endpoints in an ordered fashion. If the analysis for a secondary endpoint does not produce a statistically significant result, then the remaining secondary endpoint analyses will automatically be considered non-significant regardless of the p-value produced. In the case of an early stop or increase in sample size, the same methodology/critical value used for the primary endpoint will be applied to the key secondary endpoints for the purposes of the sequential testing. See the SAP for additional details.

The testing order for the three key secondary endpoints is as follows:

- Change from baseline in CGI-S score at Week 12.
- Change from baseline in the SDS total score at Week 12.
- Change from baseline in PROMIS SD score at Week 12.

No other adjustments for multiplicity will be made and other p-values displayed in the output will be considered for descriptive summary purposes only and will not be used for formal inference. Full details regarding the statistical analyses for the listed endpoints will be provided in the SAP.

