## 5. SAMPLE SIZE DETERMINATION

The study is planned to enroll approximately 250 patients total in a 1:1 randomization, that is, 125 patients in each of the TNX-102 SL 5.6 mg and placebo arms. [REDACTED]

The interim analysis will re-evaluate these assumptions and the IDMC may recommend a sample size increase.

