A Mixed Model Repeated Measures (MMRM) analysis will be performed for the change from baseline in CAPS-5 total score to estimate the treatment difference at Week 12. The model will include all participants in the mITT population, and the dependent variable will be the observed change from baseline in CAPS-5 total score at each post-randomization visit. Covariates in the model will include the fixed categorical effects of treatment, site, sex, and treatment by visit interaction, as well as the continuous fixed covariates of baseline score and baseline score by visit interaction. An unstructured covariance matrix will be used to model the within-subject variance-covariance errors. The Kenward-Roger approximation will be used to estimate the denominator degrees of freedom. Should the unstructured model fail to converge, an autoregressive AR(1) covariance structure will be attempted, then finally compound symmetric should AR(1) not converge.

Missing data for participants in the mITT population will be imputed via multiple imputation (MI) ([Carpenter, 2013](#); [Mallinckrodt, 2013](#)). Ten repeats of the imputation will be performed using Markov Chain Monte Carlo (MCMC) assuming non-monotone missing. Where the study medication was discontinued due to lack of efficacy, lost to follow-up, or to an AE, missing values will be imputed drawing from the baseline values, conditioned on the non-missing post-baseline values, of all participants in the mITT population under the assumption that they are missing not at random (MNAR); covariates will include site and sex. If the study medication was discontinued for any other reason, values will be imputed within treatment group using MI under the assumption that they are missing at random (MAR) with covariates for site, sex, and the CAPS-5 score recorded at each time point (including baseline). The MAR approach will also be applied for sporadic missing values (prior to discontinuation).

The test statistic based upon the least squares (LS) mean treatment difference and associated p-value [REDACTED] will be presented for each stage.

In addition, the least squares means and 95% confidence intervals (CIs) will be calculated for the treatment difference between TNX-102 SL and placebo at each time point.

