## 9.2 Secondary Efficacy Analysis

### 9.2.1 Continuous outcomes

The analyses of continuous secondary endpoints will be analyzed using an MMRM model identical to the primary endpoint, however, there will be no multiple imputation applied. These endpoints will include:

- CGI-S score.
- Change from baseline in SDS total.
- Change from baseline in participants' quality of sleep using the PROMIS Sleep Disturbance scale T-scores.
- CGI-I score
- Change from baseline in the disruption of work/school activities assessed using the SDS.
- Change from baseline in disruption of social life/ leisure activities assessed using the SDS.
- Change from baseline in the disruption of family life/home responsibilities assessed using the SDS.
- Change from baseline in CAPS-5 Arousal and Reactivity (Criterion E).
- Change from baseline in CAPS-5 Intrusion symptoms (Criterion B).
- Change from baseline in CAPS-5 Negative Cognition and Mood (Criterion D).
- Change from baseline in CAPS-5 Persistent Avoidance (Criterion C).
- Change from baseline in CAPS-5 Sleep Disturbance (item E-6).
- Mean PGIC score

- Change from baseline in CAPS-5 Reckless or Self-Destructive Behavior (item E-2).
- Changes from baseline in patient-rated Changes in Sexual Functioning Questionnaire Short-Form (CSFQ-14) in males and in females, analyzed separately
- Change from baseline in MADRS score.

The model will be changed to include the corresponding baseline value of the secondary endpoints instead of baseline CAPS-5. Randomized participants who have a baseline and at least one post-baseline assessment for the endpoint being analyzed will be included in the model. To estimate the difference between the treatment arms in CGI-I and PGIC scores (which do not have baseline assessments), the same method will be used, however, with the observed baseline response and associated interactions removed from the list of covariates. All visits will be included in the analysis. P-values from these comparisons will be considered nominal (conclusions from the sequential testing algorithm will be reported separately).

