### **9.2.2 Categorical outcomes**

Binary data over time will be analyzed using a Cochran Mantel Haenszel (CMH) test stratified by presence of current major depressive episode. Examples include the CGI-I and the PGIC, in which responders are defined as those who score ‘2’ (much improved) or ‘1’ (very much improved) on these 7-point scales. Participants with missing data will be analyzed as though they are non-responders. This will be reported for each visit with the primary time point of interest at Week 12 (with remission spanning data at weeks 8 and 12). Odds ratios for treatment contrasts along with two-sided 95% CIs will also be reported. Two-sided p-values for the test of no difference between the TNX-102 SL and placebo will be provided.

These endpoints will include:

- Proportion of participants with a PGIC score of “much improved” or “very much improved”.
- Proportion of participants with a CGI-I score of “much improved” or “very much improved”.
- Proportion of participants with a CAPS-5 total score of 0 –10 (asymptomatic/few symptoms).

- Proportion of participants with a CAPS-5 total score of 0-22 (asymptomatic or mild PTSD/subthreshold).
- Proportion of participants with Response, defined as a  $\geq$  10-point improvement from baseline in CAPS-5 total score.
- Proportion of participants with Loss of Diagnosis, defined as Response AND no longer meeting DSM-5 symptom criteria in any one or more of the four clusters (B, C, D, E).
- Proportion of participants in Remission, defined as Loss of Diagnosis AND Total CAPS-5 score  $\leq$  10.
- Proportion of participants achieving sustained Remission, defined as Loss of Diagnosis AND Total CAPS-5 score  $\leq$  10 after both 8 weeks AND 12 weeks of treatment.
- Proportion of participants with a  $\geq$ 50% improvement from baseline in CAPS-5 total score.

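### CGI-I, PGIC and the CAPS-5 0–22 endpoint are compared without a baseline PTSD-severity term, at a small cost in precision

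*SAP*

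**What the plan says.** The primary model in SAP 9.1.1 adjusts for baseline CAPS-5 and its visit interaction as well as the categorical terms: "Covariates in the model will include the fixed categorical effects of treatment, site, sex, and treatment by visit interaction". SAP 9.2.1 carries this model over to the continuous secondary endpoints and replaces baseline CAPS-5 with the baseline of the endpoint analyzed. CGI-I and PGIC are the exception. They are fitted "with the observed baseline response and associated interactions removed from the list of covariates", with no substitute. Protocol 13.4.3 leaves the matter open: "baseline score and baseline score by visit interaction will be included as appropriate".

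For responder endpoints SAP 9.2.2 says: "Binary data over time will be analyzed using a Cochran Mantel Haenszel (CMH) test". The only stratifier is current major depressive episode (MDE): "test stratified by presence of current major depressive episode". Protocol 13.4.3 and the synopsis control for sex instead, and SAP 12 states that nothing departs from the protocol. Neither document puts baseline CAPS-5 or CGI-S into a responder analysis.

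Both measures are available. Protocol 10.2.1 schedules the baseline rating ("Physician to assess CGI-S"). A Visit 2 CAPS-5 of at least 33 is a condition of randomization (Protocol 8.4), and the mITT definition requires a baseline CAPS-5.

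**The concern.** A scale that measures change has no baseline, but the patient's severity at entry may still predict the score. The plan adjusts every other continuous secondary endpoint for a baseline, and the investigator rates CGI-S beside CGI-I at the same post-baseline visits. Dropping severity altogether therefore looks like a side effect of the wording.

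The 0–22 endpoint is the clearest binary case because its threshold is absolute. From a baseline of 33 a patient needs a fall of 33 − 22 = 11 points to reach it. From 55 the fall needed is 55 − 22 = 33 points. If one arm happens to start more severe, its 0–22 rate drops, and stratifying by MDE or sex corrects this only so far as those factors track CAPS-5. At stake is the precision of reported estimates and their freedom from chance imbalance. The tests themselves remain valid.

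**Working it through.** **Inputs from the documents.** "125 patients in each of the TNX-102 SL 5.6 mg and placebo arms" (SAP 5); "significance tests of treatment differences will be tested at the two-sided 0.05 level" (Protocol 13); the baseline floor of 33; the threshold of 22. The effect size, SD and power behind the sample of 250 are redacted, so that figure cannot be reproduced. No power is stated for the endpoints discussed here.

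**Assumed inputs.** The correlation of baseline severity with outcome, the SDs, the response rates and the starting power are all assumptions, varied below.

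**1. CGI-I and PGIC.** A covariate with correlation ρ multiplies the residual variance by 1 − ρ². Assume 80% power without it. The standardized effect is then d = (1.960 + 0.842) × √(2/125) = 0.354. With the covariate, power = Φ(2.802/√(1 − ρ²) − 1.960), and the gain is worth an unadjusted sample of 250/(1 − ρ²).

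| ρ | 1 − ρ² | Power | Gain (points) | Equivalent N |
|---|---|---|---|---|
| 0.1 | 0.99 | 80.4% | 0.4 | 253 |
| 0.2 | 0.96 | 81.6% | 1.6 | 260 |
| 0.3 | 0.91 | 83.6% | 3.6 | 275 |

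Starting from 90% power, the same three values give 90.3%, 91.1% and 92.5%.

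**2. CAPS-5 0–22.** The simulated model has 125 per arm, baseline truncated at 33, Week 12 score = mean + slope × baseline + effect + error, and response if the score is 22 or less. Each cell shows power without baseline CAPS-5, then from logistic regression that adds it.

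| Assumptions | r = 0.23 | r = 0.38 | r = 0.50 |
|---|---|---|---|
| A: baseline SD about 7, rates about 27% vs 41%, CMH by sex, 3000 trials | 69 → 70% | 65 → 70% | 60 → 66% |
| B: rates about 25–29% vs 41–43%, CMH by sex, 3000 trials (r = 0.24, 0.39, 0.52) | 75.2 → 76.0% | 72.3 → 75.0% | 66.3 → 73.5% |
| C: baseline SD 6.7, Week 12 SD 12.5, effect 5 points, unstratified test, 1200 trials | 71 → 73% | 69 → 74% | 68 → 74% |
| D: same type of model | 68.5 → 69.3% | 68.5 → 72.1% | 70.1 → 74.3% |

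The gain is about 1 to 6 points; set B reaches 7 at r = 0.52. At the lowest correlation it is close to simulation error (about 1.3 points in set C). In set B the two-sided type I error was 4.5–5.5% for CMH and 5.0–5.6% for logistic regression.

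**3. Other CAPS-5 thresholds (set C).**

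| Endpoint | r = 0.23 | r = 0.38 | r = 0.50 |
|---|---|---|---|
| Response, 10 points or more | 64 → 67% | 73 → 73% | 77 → 77% |
| Reduction of 30% or more | 69 → 70% | 76 → 77% | 80 → 80% |
| Reduction of 50% or more | 71 → 71% | 74 → 74% | 78 → 79% |
| 0–10 (about 6% vs 13%) | 43 → 41% | 45 → 44% | 47 → 47% |

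The slope explains the pattern for Response. The regression of Week 12 score on baseline has slope r × 12.5/6.7 = 0.43, 0.71 and 0.93. The slope for change from baseline is that minus 1: −0.57, −0.29 and −0.07. As baseline comes to predict the Week 12 score better, it has less left to predict in the change. The 0–10 endpoint has few events, and Remission is built on it.

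**4. Chance imbalance.** With set C's SDs, a baseline difference at the edge of its 95% chance range shifts the expected Week 12 difference by r × 12.5 × √(2/125) × 1.96 = 3.10r. That is 0.7, 1.2 and 1.5 points at r = 0.23, 0.38 and 0.50, against the assumed effect of 5.

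**The case against.** The strongest reply is that nothing formal depends on these endpoints. They lie outside the fixed sequence, SAP 7.1.1.1 makes their p-values descriptive, and the primary and key secondary models already adjust for baseline. This stands, and it sets the priority.

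Next, the correlations are assumed and may be low. CGI-I and PGIC already ask about change, and the entry floor of 33 narrows the range of baseline CAPS-5. At ρ of 0.2 or less the gain for these scores is under 2 points. This also stands. In addition, the simulated models include no dropout, whereas the SAP counts missing patients as non-responders. That would usually weaken the link between baseline and response.

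Protocol 13.4.3 also makes an exception for scales without a baseline. That exception concerns the dependent variable. On covariates the protocol says only that baseline terms enter where appropriate, so a substitute is permitted though not required.

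A reader might infer that every responder endpoint gives away power. Step 3 does not support this: Response and the percentage reductions already use the patient's own baseline, and 0–10 gains nothing. A reader might also infer that these analyses use no baseline information at all. They do: site and sex stay in the MMRM, and MDE (SAP) or sex (protocol) stays in the CMH test. Sets A and B used the protocol's stratifier, set C used none, and no set is documented as using the SAP's MDE stratifier.

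**Conclusion.** The point holds in a limited form. CGI-I, PGIC and CAPS-5 0–22 are compared without a baseline PTSD-severity term although suitable measures are in the database. The cost is some precision and exposure to chance imbalance: about 0.4 to 3.6 power points for CGI-I and PGIC (ρ = 0.1–0.3, starting from 80% power) and about 1 to 6 points for 0–22 (r = 0.23–0.50, complete data). Every correlation, SD and response rate is an assumption. For Response, percentage reduction, 0–10 and Remission the case is not made. Remission and Loss of Diagnosis were not simulated directly; they are built on 0–10 and Response.

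The documents do not support reading this as a threat to the trial's conclusions or to the validity of the planned tests. It is a low-priority improvement to descriptive estimates.

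**What to change.** - **SAP 9.2.1:** for CGI-I, add baseline CGI-S and its visit interaction. For PGIC, add baseline CAPS-5 total and its visit interaction. State how a missing baseline CGI-S is handled, since the mITT definition guarantees only a baseline CAPS-5.
- **SAP 9.2.2:** first reconcile the stratifier, which is MDE here and sex in Protocol 13.4.3. Then analyze CAPS-5 0–22 by logistic regression with treatment, that stratifier and baseline CAPS-5. Report the standardized risk difference with its 95% CI beside the odds ratio.
- Leave CMH in place for Response, percentage reduction, 0–10 and Remission.

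The cost is SAP wording and programming, with no new data or patients. The drawback is that the odds ratio becomes conditional on baseline CAPS-5, which is why the standardized risk difference goes with it. The change should be fixed before unblinding so that it cannot look data-driven.

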### **9.2.2 Categorical outcomes**

Binary data over time will be analyzed using a Cochran Mantel Haenszel (CMH) test stratified by presence of current major depressive episode. Examples include the CGI-I and the PGIC, in which responders are defined as those who score ‘2’ (much improved) or ‘1’ (very much improved) on these 7-point scales. Participants with missing data will be analyzed as though they are non-responders. This will be reported for each visit with the primary time point of interest at Week 12 (with remission spanning data at weeks 8 and 12). Odds ratios for treatment contrasts along with two-sided 95% CIs will also be reported. Two-sided p-values for the test of no difference between the TNX-102 SL and placebo will be provided.

These endpoints will include:

- Proportion of participants with a PGIC score of “much improved” or “very much improved”.
- Proportion of participants with a CGI-I score of “much improved” or “very much improved”.
- Proportion of participants with a CAPS-5 total score of 0 –10 (asymptomatic/few symptoms).

- Proportion of participants with a CAPS-5 total score of 0-22 (asymptomatic or mild PTSD/subthreshold).
- Proportion of participants with Response, defined as a  $\geq$  10-point improvement from baseline in CAPS-5 total score.
- Proportion of participants with Loss of Diagnosis, defined as Response AND no longer meeting DSM-5 symptom criteria in any one or more of the four clusters (B, C, D, E).
- Proportion of participants in Remission, defined as Loss of Diagnosis AND Total CAPS-5 score  $\leq$  10.
- Proportion of participants achieving sustained Remission, defined as Loss of Diagnosis AND Total CAPS-5 score  $\leq$  10 after both 8 weeks AND 12 weeks of treatment.
- Proportion of participants with a  $\geq$ 50% improvement from baseline in CAPS-5 total score.

## 10. SAFETY AND TOLERABILITY ANALYSIS

The safety analysis will be run on the Safety population. The analysis of safety assessments in this study will include summaries of the following safety and tolerability data collected for each participant:

- Adverse Events
- Clinical Laboratory Investigations
- C-SSRS
- Vital Signs
- Visual Examinations of Oral Cavity
- Electrocardiogram (ECG) Parameters (Obtained at Screening only)
- Changes from baseline in participant-rated CSFQ-14
- MADRS

Summaries of continuous parameters will include raw values and change from baseline, as appropriate. Listings of safety data will also be presented.

### 10.1 Adverse Events

All AEs, treatment-emergent adverse events (TEAEs), and SAEs will be coded using MedDRA, version 21.0.

TEAEs are defined as either new onset AEs with an onset at the time of or following the start of treatment through ten days after the last dose of study medication, or a recurrence of an AE (or medical history) present prior to randomization but increasing in severity, frequency or relationship at the time of or following the start of treatment

An AE summary table will be presented for the following:

- TEAEs by severity

- TEAEs leading to study drug discontinuation
- TEAEs by relationship
- SAEs
- Oral Cavity AEs

Summaries of incidence rates (frequencies and percentages) of individual AEs by MedDRA SOC and preferred term will be prepared. Such summaries will be displayed for all TEAEs, TEAEs by maximum severity, and TEAEs by strongest relationship to study drug.

Each participant will be counted only once within each summation level (SOC; preferred term). If a participant experiences more than one TEAE within each summation level only, the TEAE with the strongest relationship or the maximum severity, as appropriate, will be included in the summaries of relationship and severity.

Additionally, a summary of the Oral Cavity AE characteristics will be presented; this includes information such as temporal proximity to the dose, duration and whether the AE was present the following morning.

Adverse events of special interest pertaining to abuse potential (as defined in the January 2017 Assessment of Abuse Potential for Drugs – Guidance for Industry) will be analyzed separately by treatment group, SOC and preferred term, and displayed in tabular format.

In the AE data listings, all AEs will be displayed. AEs that are treatment-emergent will be flagged.

#### **10.1.1 Adverse Events Leading to Discontinuation of Study Drug**

A summary of incidence rates (frequencies and percentages) of TEAEs leading to discontinuation of study drug by treatment group, SOC, and preferred term will be prepared for the Safety population.

A data listing of AEs leading to discontinuation of study drug will also be provided, displaying details of the event(s) captured on the CRF.

